1. EVALUATION OF LESIONS

Solid tumors will be evaluated using Response Evaluation Criteria In Solid Tumors version 1.1 (RECIST 1.1) guideline with BMS modifications.¹

At baseline, tumor lesions/lymph nodes will be categorized measurable or non-measurable as follows:

1.1 Measurable

Tumor lesions: Must be accurately measured in at least one dimension (longest diameter in the plane of the measurement to be recorded) with a minimum size of:

10 mm by CT/MRI scan - (scan slice thickness no greater than 5 mm), or \geq 2x slice thickness if greater than 5 mm.

Malignant lymph nodes: To be considered pathologically enlarged and measurable, a lymph node must be ≥ 15 mm in short axis when assessed by CT/MRI scan (scan slice thickness recommended to be no greater than 5 mm).

Lymph nodes merit special mention since they are normal anatomical structures which may be visible by imaging even if not involved by tumor. Pathological nodes which are defined as measurable and may be identified as target lesions must meet the criterion of a short axis of ≥ 15 mm by CT/MRI scan. Only the short axis of these nodes will contribute to the baseline sum. The short axis of the node is the diameter normally used by radiologists to judge if a node is involved by solid tumor. Nodal size is normally reported as two dimensions in the plane in which the image is obtained (for CT scan this is almost always the axial plane; for MRI the plane of acquisition may be axial, sagittal or coronal). The smaller of these measures is the short axis. For example, an abdominal node which is reported as being 20 mm x 30 mm has a short axis of 20 mm and qualifies as a malignant, measurable node. In this example, 20 mm should be recorded as the node measurement. All other pathological nodes (those with short axis ≥ 10 mm but ≤ 15 mm) should be considered non-target lesions. Nodes that have a short axis ≤ 10 mm are considered non-pathological and should not be recorded or followed.

Note: Lesions on X-Ray are not to be selected as Target or Non-Target Lesions.

1.2 Non-measurable

All other lesions are considered non-measurable, including small lesions (longest diameter < 10 mm or pathological lymph nodes with ≥ 10 to < 15 mm short axis), as well as truly non-measurable lesions. Lesions considered truly non-measurable include: leptomeningeal disease, inflammatory breast disease, lymphangitic involvement of skin or lung, abdominal masses/abdominal organomegaly identified by physical exam that in not measurable by reproducible imaging techniques.

Note: Lesions on X-Ray are not to be selected as Target or Non-Target Lesions.

1.3 Special considerations regarding lesion measurability

1.3.1 Bone lesions

 Bone scan, PET scan or plain films are *not* considered adequate imaging techniques to measure bone lesions. However, these techniques can be used to confirm the presence or disappearance of bone lesions.

- Lytic bone lesions or mixed lytic-blastic lesions, with *identifiable soft tissue components*, that can be evaluated by cross sectional imaging techniques such as CT or MRI can be considered as measurable lesions if the *soft tissue component* meets the definition of measurability described above.
- Blastic bone lesions are non-measurable.

1.4 Baseline Documentation Of 'Target' And 'Non-Target' Lesions

When more than one measurable lesion is present at baseline all lesions up to a maximum of five lesions total (and a maximum of two lesions per organ) representative of all involved organs should be identified as target lesions and will be recorded and measured at baseline (this means in instances where patients have only one or two organ sites involved a maximum of two and four lesions respectively will be recorded).

Note: A maximum of two lesions can be selected per organ system. For example, a maximum of two lung lesions can be selected (selected from one lung or one lesion from each). A maximum of two lymph nodes can be selected at baseline, as the lymphatic system is considered one organ.

Target lesions should be selected on the basis of their size (lesions with the longest diameter), be representative of all involved organs, but in addition should be those that lend themselves to reproducible repeated measurements. It may be the case that, on occasion, the largest lesion does not lend itself to reproducible measurement in which circumstance the next largest lesion which can be measured reproducibly should be selected.

A sum of the diameters (longest for non-nodal lesions, short axis for nodal lesions) for all target lesions will be calculated and reported as the baseline sum diameters. If lymph nodes are to be included in the sum, then as noted above, only the short axis is added into the sum. The baseline sum diameters will be used as reference to further characterize any objective tumor regression in the measurable dimension of the disease.

All other lesions (or sites of disease) including pathological lymph nodes should be identified as non-target lesions and should also be recorded at baseline. Measurements are not required and these lesions should be followed as 'present', 'absent', or in rare cases 'unequivocal progression' (more details to follow). In addition, it is possible to record multiple non-target lesions involving the same organ as a single item on the case record form (eg, 'multiple enlarged pelvic lymph nodes' or 'multiple liver metastases').

2. RESPONSE CRITERIA

2.1 Evaluation of Target lesions

• Complete Response (CR): Disappearance of all target lesions. Any pathological lymph nodes (whether target or non-target) must have reduction in short axis to < 10 mm.

- Partial Response (PR): At least a 30% decrease in the sum of diameters of target lesions, taking as reference the baseline sum diameters.
- **Progressive Disease (PD):** At least a 20% increase in the sum of diameters of target lesions, taking as reference the smallest sum on study (this includes the baseline sum if that is the smallest on study). In addition to the relative increase of 20%, the sum must also demonstrate an absolute increase of at least 5 mm. (Note: the appearance of one or more new lesions is also considered progression).
- **Stable Disease (SD):** Neither sufficient shrinkage to qualify for PR nor sufficient increase to qualify for PD, taking as reference the smallest sum diameters while on study.
- Not Evaluable (NE): If one or more target lesions cannot be measured or adequately assessed as either fully resolved or too small to measure (due to missing or poor quality images), and the sum of diameters of the remaining measured target lesions (if any) has not increased sufficiently to meet Progressive Disease as defined above.

2.1.1 Special Notes on the Assessment of Target Lesions

2.1.1.1 Lymph nodes

Lymph nodes identified as target lesions should always have the actual short axis measurement recorded (measured in the same anatomical plane as the baseline examination), even if the nodes regress to below 10 mm on study. This means that when lymph nodes are included as target lesions, the 'sum' of lesions may not be zero even if complete response criteria are met, since a normal lymph node is defined as having a short axis of < 10 mm. Case report forms or other data collection methods may therefore be designed to have target nodal lesions recorded in a separate section where, in order to qualify for CR, each node must achieve a short axis < 10 mm. For PR, SD and PD, the actual short axis measurement of the nodes is to be included in the sum of target lesions.

2.1.1.2 Target lesions that become 'too small to measure'

While on study, all lesions (nodal and non-nodal) recorded at baseline should have their actual measurements recorded at each subsequent evaluation, even when very small (eg, 2 mm). However, sometimes lesions or lymph nodes which are recorded as target lesions at baseline become so faint on CT scan that the radiologist may not feel comfortable assigning an exact measure and may report them as being 'too small to measure'. When this occurs it is important that a value be recorded on the case report form. If it is the opinion of the radiologist that the lesion has likely disappeared, the measurement should be recorded as 0 mm. If the lesion is believed to be present and is faintly seen but too small to measure, a default value of 5 mm should be assigned as the reference diameter. (Note: It is less likely that this rule will be used for lymph nodes since they usually have a definable size when normal and are frequently surrounded by fat such as in the retroperitoneum; however, if a lymph node is believed to be present and is faintly seen but too small to measure, a default value of 5 mm should be assigned in this circumstance as well). This

default value is derived from the 5 mm CT slice thickness (but should not be changed with varying CT slice thickness). The measurement of these lesions is potentially non-reproducible, therefore providing this default value will prevent false responses or progressions based upon measurement error. To reiterate, however, if the radiologist is able to provide an actual measure, that should be recorded, even if it is below 5 mm.

2.1.1.3 Lesions that split or coalesce on treatment

When non-nodal lesions 'fragment', the longest diameters of the fragmented portions should be added together to calculate the target lesion sum. Similarly, as lesions coalesce, a plane between them may be maintained that would aid in obtaining maximal diameter measurements of each individual lesion. If the lesions have truly coalesced such that they are no longer separable, the vector of the longest diameter in this instance should be the maximal longest diameter for the 'coalesced lesion'.

2.2 Evaluation of Non-target lesions

This section provides the definitions of the criteria used to determine the tumor response for the group of non-target lesions. While some non-target lesions may actually be measurable, they need not be measured and instead should be assessed only qualitatively at the time points specified in the protocol.

- Complete Response (CR): Disappearance of all non-target lesions. All lymph nodes must be non-pathological in size (< 10mm short axis).
- Non-CR/Non-PD: Persistence of one or more non-target lesion(s)
- **Progressive Disease (PD):** Unequivocal progression of existing non-target lesions.

2.2.1 Special Notes on Assessment of Progression of Non-Target Disease

The concept of progression of non-target disease requires additional explanation as follows:

2.2.1.1 When the patient also has measurable disease

In this setting, to achieve 'unequivocal progression' on the basis of the non-target disease, there must be an overall level of substantial worsening in non-target disease such that, even in presence of SD or PR in target disease, the overall tumor burden has increased sufficiently to merit discontinuation of therapy A modest 'increase' in the size of one or more non-target lesions is usually not sufficient to qualify for unequivocal progression status. Pleural effusions, pericardial effusions and ascites will not be followed as target or non-target lesions and will not contribute to response or progression. The designation of overall progression solely on the basis of change in non-target disease in the face of SD or PR of target disease will therefore be extremely rare.

2.2.1.2 When the patient has only non-measurable disease

This circumstance arises in some trials when it is not a criterion of study entry to have measurable disease. The same general concepts apply here as noted above, however, in this instance there is no measurable disease assessment to factor into the interpretation of an increase in non-measurable disease burden. Because worsening in non-target disease cannot be easily quantified (by definition: if all lesions are truly non-measurable) a useful test that can be applied when assessing patients for unequivocal progression is to consider if the increase in overall disease burden based on the change

in non-measurable disease is comparable in magnitude to the increase that would be required to declare PD for measurable disease: ie, an increase in tumor burden representing an additional 73% increase in 'volume' (which is equivalent to a 20% increase diameter in a measurable lesion). Examples include, an increase in lymphangitic disease from localized to widespread, or may be described as 'sufficient to require a change in therapy'. If 'unequivocal progression' is seen, the patient should be considered to have had overall PD at that point. While it would be ideal to have objective criteria to apply to non-measurable disease, the very nature of that disease makes it impossible to do so; therefore the increase must be substantial.

2.2.2 New Lesions

The appearance of new malignant lesions denotes disease progression; therefore, some comments on detection of new lesions are important. There are no specific criteria for the identification of new radiographic lesions; however, the finding of a new lesion should be unequivocal: ie, not attributable to differences in scanning technique, change in imaging modality or findings thought to represent something other than tumor (for example, some 'new' bone lesions may be simply healing or flare of pre-existing lesions). This is particularly important when the patient's baseline lesions show partial or complete response. For example, necrosis of a liver lesion may be reported on a CT scan report as a 'new' cystic lesion, which it is not.

NOTE: Fluid collections (pleural effusions, pericardial effusions, and ascites) will not be considered new lesions and will not contribute to response or progression. In the event a new fluid collection is seen on a post-baseline imaging exam, a comment may be made, but the appearance of a new fluid collection alone should not result in an assessment of Progressive Disease (PD). A lesion identified on a follow-up study in an anatomical location that was not scanned at baseline is considered a new lesion and will indicate disease progression. An example of this is the patient who has visceral disease at baseline and while on study has a CT or MRI brain ordered which reveals metastases. The patient's brain metastases are considered to be evidence of PD even if he/she did not have brain imaging at baseline. A lesion identified on Chest X-Ray that was not present in prior CT can be considered a new lesion and will result in Progressive Disease (PD).

If a new lesion is equivocal, for example because of its small size, continued follow-up evaluation will clarify if it represents truly new disease. If repeat scans confirm there is definitely a new lesion, then progression should be declared using the date of the initial scan. While FDG-PET response assessments need additional study, it is sometimes reasonable to incorporate the use of FDG-PET scanning to complement CT scanning in assessment of progression (particularly possible 'new' disease). New lesions on the basis of FDG-PET imaging can be identified according to the following algorithm:

- 1. Negative FDG-PET at baseline, with a positive FDG-PET at follow-up is a sign of PD based on a new lesion.
- 2. No FDG-PET at baseline and a positive FDG-PET at follow-up: If the positive FDG-PET at follow-up corresponds to a new site of disease confirmed by CT, this is PD. If the positive FDG-PET at follow-up is not confirmed as a new site of disease on CT, additional follow-up CT scans are needed to determine if there is truly progression occurring at that site (if so, the date of PD will be the date of the initial abnormal FDG-PET scan). If the positive FDG-PET

Clinical Protocol CA209142 BMS-936558 nivolumab

at follow-up corresponds to a pre-existing site of disease on CT that is not progressing on the basis of the anatomic images, this is not PD.

2.3 Response Assessment

2.3.1 Evaluation of Best Overall Response

The best overall response is the best response recorded from the start of the study treatment until disease progression or the last response recorded, taking into account any requirement for confirmation and censoring rules regarding subsequent therapy. The patient's best overall response assignment will depend on the findings of both target and non-target disease and will also take into consideration the appearance of new lesions. Furthermore, depending on the nature of the study and the protocol requirements, it may also require confirmatory measurement.

2.3.2 Time Point Response

At each protocol specified time point, a response assessment occurs. Table 2.3.2-1 provides a summary of the overall response status calculation at each time point for patients who have measurable disease at baseline. When patients have non-measurable (therefore non-target) disease only, Table 2.3.2-2 is to be used.

Table 2.3.2-1: Time Point Response: Patients With Target (± Non-Target) Disease				
Target Lesions	Non-Target Lesions	New Lesions	Overall Response	
CR	CR	No	CR	
CR	Non-CR/non-PD	No	PR	
CR	Not evaluated	No	PR	
PR	Non-PD or not all evaluated	No	PR	
SD	Non-PD or not all evaluated	No	SD	
Not all evaluated	Non-PD	No	NE	
PD	Any	Yes or No	PD	
Any	PD	Yes or No	PD	
Any	Any	Yes	PD	

CR = complete response, PR = partial response, SD = stable disease, PD = progressive disease and NE = inevaluable

Table 2.3.2-2: Time Point Re	Time Point Response: Patients with Non-target Disease Only		
Non-Target Lesions	New Lesions	Overall Response	
CR	No	CR	
Non-CR/non-PD	No	Non-CR/non-PD ^a	
Not all evaluated	No	NE	

Protocol Amendment No: 09

Date: 27-Aug-2021 231

Table 2.3.2-2: Time Point Response: Patients with Non-target Disease Only			
Non-Target Lesions New Lesions Overall Response			
Unequivocal PD	Yes or No	PD	
Any Yes PD			
CR = complete response, PD = progressive disease and NE = inevaluable			

Non-CR/non-PD is preferred over SD for non-target disease since SD is increasingly used as endpoint for assessment of efficacy in some trials so to assign this category when no lesions can be measured is not advised.

2.3.3 Best Overall Response

Best response determination of complete or partial response requires confirmation: Complete or partial responses may be claimed only if the criteria for each are met at a subsequent time point of ≥ 4 weeks (28 days) later. In this circumstance, the best overall response can be interpreted as in Table 2.3.3-1. When SD is believed to be best response, it must meet the protocol specified minimum time from the date of first treatment or randomization date.

For example, if the first scheduled follow-up imaging visit is Week 6 (\pm 7 days) for a particular protocol, a Best Response of SD can only be made after the subject is on-study for a minimum of 6 weeks (42 days) minus 7 days, for an absolute minimum time on-study of 35 days from the reference start date (reference date is considered Day 1 on study). If the subject is not on-study for at least this amount of time, any tumor assessment indicating stable disease before this time period will have a Best Response of NE unless PD is identified.

Special note on response assessment: When nodal disease is included in the sum of target lesions and the nodes decrease to 'normal' size (< 10 mm), they may still have a measurement reported on scans. This measurement should be recorded even though the nodes are normal in order not to overstate progression should it be based on increase in size of the nodes. As noted earlier, this means that patients with CR may not have a total sum of 'zero' on the case report form (CRF).

Table 2.3.3-1:	2.3.3-1: Best Overall Response (Confirmation of CR and PR Required)			
Overall Response First Time Point	Overall Response Subsequent Time Point	Best Overall Response		
CR	CR	CR		
CR	PR	SD, PD OR PR ^a		
CR	SD	SD provided minimum criteria for SD duration met, otherwise, PD		
CR	PD	SD provided minimum criteria for SD duration met, otherwise, PD		
CR	NE	SD provided minimum criteria for SD duration met, otherwise, NE		
PR	CR	PR		

Protocol Amendment No: 09

Date: 27-Aug-2021 232

Table 2.3.3-1:	Best Overall Response (Confirmation of CR and PR Required)			
Overall Response First Time Point	Overall Response Subsequent Time Point	Best Overall Response		
PR	PR	PR		
PR	SD	SD		
PR	PD	SD provided minimum criteria for SD duration met, otherwise, PD		
PR	NE	SD provided minimum criteria for SD duration met, otherwise, NE		
NE	NE	NE		
CR = complete response, PR = partial response, SD = stable disease, PD = progressive disease, and				
NE = inevaluable				

^a If a CR is truly met at first time point, then any disease seen at a subsequent time point, even disease meeting PR criteria relative to baseline, makes the disease PD at that point (since disease must have reappeared after CR). Best response would depend on whether minimum duration for SD was met. However, sometimes 'CR' may be claimed when subsequent scans suggest small lesions were likely still present and in fact the patient had PR, not CR at the first time point. Under these circumstances, the original CR should be changed to PR and the best response is PR.

2.3.4 Confirmation Scans

Verification of Response: To be assigned a status of CR or PR, changes in tumor measurements must be confirmed by consecutive or subsequent repeat assessments that should be performed no less than 28 days after the criteria for response are first met. Subsequent documentation of a CR may provide confirmation of a previously identified CR even with an intervening NE or PR (eg, CR NE CR or CR PR CR). Subsequent documentation of a PR may provide confirmation of a previously identified PR even with an intervening NE or SD (eg, PR NE PR or PR SD PR). However, only one (1) intervening time point will be allowed between PR/CRs for confirmation.

Verification of Progression: Progression of disease should be verified in cases where progression is equivocal. If repeat scans confirm PD, then progression should be declared using the date of the initial scan. If repeat scans do not confirm PD, then the subject is considered to not have progressive disease.

REFERENCES

¹ Eisenhauer EA, Therasse P, Bogaerts J, et al. New response evaluation criteria in solid tumors: revised RECIST guideline (version 1.1). Eur J Cancer 2009; 45: 228-47.

Clinical Protocol CA209142 BMS-936558 nivolumab

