8.3 Endpoints

8.3.1 Primary Endpoint(s)

The primary objective will be measured by the primary endpoint of investigator-assessed ORR in each cohort. It is defined as the number of subjects with a best overall response (BOR) of confirmed CR or PR, according to RECIST 1.1 criteria, divided by the number of treated subjects in the related cohort. The final analysis of the primary endpoint will occur at least 6 months after the last enrolled subject's first dose of study therapy. The BOR is defined as the best response designation recorded between the date of first dose and the date of initial objectively documented progression per RECIST v1.1 or the date of subsequent therapy, whichever occurs first. For subjects without documented progression or subsequent therapy, all available response designations will contribute to the BOR determination. For purposes of analysis, if a subject receives one dose and discontinues the study without assessment or receives subsequent therapy prior to assessment, this subject will be counted in the denominator (as non-respondent.)

The investigator-assessed ORR will be further characterized by the investigator assessed duration of response (DOR) and rate of complete response (CR). DOR is defined as the time from first confirmed response (CR or PR) to the date of the first documented tumor progression as determined using RECIST 1.1 criteria or death due to any cause, whichever occurs first. For subjects who neither progress nor die, the DOR censoring will be the same as PFS censoring (see Section 8.3.3). In each cohort, DOR will be computed for subjects with a BOR of PR or CR.

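### Appendix 3 allows CR, PR, CR as a confirmed complete response in one rule and excludes it in another when disease is seen at the middle scan, so the complete response rate depends on which rule is applied

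*Combined protocol and SAP*

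**What the plan says.** Section 2.3.4 of Appendix 3 covers confirmation. A repeat CR at least 28 days later may confirm an earlier CR "even with an intervening NE or PR (eg, CR NE CR or CR PR CR". The section sets one limit: "However, only one (1) intervening time point will be allowed between PR/CRs for confirmation". The sequence CR, PR, CR meets it.

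Table 2.3.3-1 in Section 2.3.3 lists SD, PD or PR as the BOR for CR followed by PR; CR is not listed. Footnote a gives two branches.

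- If the CR was truly met, disease at a later scan, "even disease meeting PR criteria relative to baseline, makes the disease PD at that point".
- If later scans suggest that small lesions had been there all along, "Under these circumstances, the original CR should be changed to PR and the best response is PR".

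The main text builds the endpoints on these calls. Under Section 8.3.1, BOR is the "best response designation recorded between the date of first dose and the date of initial objectively documented progression per RECIST v1.1" or subsequent therapy, whichever is earlier. The same section states: "The investigator-assessed ORR will be further characterized by the investigator assessed duration of response (DOR) and rate of complete response (CR". Section 8.4.2.1 reports CRR with a 95% exact confidence interval. DOR, which is computed only for subjects whose BOR is CR or PR, follows this rule: "DOR is defined as the time from first confirmed response (CR or PR) to the date of the first documented tumor progression", or death. PFS (Section 8.3.3) runs from first dose to first documented progression or death.

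**The concern.** Section 2.3.4 and footnote a both apply to a subject read as CR, then PR with disease visible, then CR. They give different best responses. Two readers with identical scans could each follow Appendix 3 and disagree, and so could two programmers deriving BOR from the same time-point calls.

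CRR is the quantity most exposed. It is one of the two named characterisations of the primary endpoint, and both branches of footnote a remove the confirmed CR that Section 2.3.4 grants. Under the PD branch the progression date also moves, which can carry over to PFS, DOR and ORR. The re-initiation endpoints are defined in the same way (Section 8.3.3), so they inherit the ambiguity.

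**Working it through.** The plan gives no figure for this point, so the check applies each rule to specific sequences. BOR is closed at the first PD, as Section 8.3.1 requires.

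**Sequence CR, PR, CR, with disease seen at scan 2**

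| Rule | Scans as read | BOR | Responder | Progression |
|---|---|---|---|---|
| Section 2.3.4 | CR, PR, CR | CR | yes | none |
| Footnote a, true CR | CR, PD, CR | SD if the minimum SD duration is met, otherwise PD | no | scan 2 |
| Footnote a, misread CR | PR, PR, CR | PR | yes | none |

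In the second row the later CR falls outside the BOR window. There is no confirmed response, so no DOR is computed. In the third row the last CR has no earlier CR left to confirm it, so BOR stays PR unless a further CR follows.

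**Sequence PR, CR, PR, CR, with disease seen at scan 3**

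Table 2.3.3-1 makes PR followed by CR a confirmed PR, so the subject is already a responder.

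| Rule | BOR | Responder | Progression |
|---|---|---|---|
| Section 2.3.4 | CR | yes | none |
| Footnote a, true CR | PR | yes | scan 3; DOR and PFS end there |
| Footnote a, misread CR | PR | yes | none |

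**Which endpoint changes, relative to Section 2.3.4**

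- CRR: under both branches of footnote a, in both sequences.
- PFS date: under the PD branch only.
- ORR: under the PD branch only, and only without an earlier confirmed response.
- DOR: shortened under the PD branch only when there was an earlier confirmed response. In CR, PR, CR read as PD there is no DOR to shorten.

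**Size per subject (planned sample sizes, Section 8.1)**

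- Two-stage arms: 1/48 = 2.1 percentage points.
- Cohorts C5 and C6: 1/40 = 2.5 points.
- Cohort C3: 1/30 = 3.3 points.

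Where ORR changes, it moves by the same amount. One subject then matters only at a boundary. In a two-stage arm, 20/48 = 41.7% becomes 19/48 = 39.6%, below the 20 responses needed to reject the null. In C5 the Clopper-Pearson lower limit is the 0.025 quantile of Beta(x, n − x + 1). For 16/40 this reproduces the plan's 24.9%; for 15/40 it is 22.7%, below the 23% background rate that the plan cites.

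**The case against.** The strongest defence is that the rules differ in scope. Table 2.3.3-1 maps pairs of scans, while Section 2.3.4 deals with three. The table also gives SD for PR followed by SD, and SD or NE for CR followed by NE, yet Section 2.3.4 allows PR, SD, PR and CR, NE, CR as confirmed. Nobody would call those contradictions, because the third scan supplies the confirmation. That disposes of the table cell taken alone. It does not dispose of footnote a, which either labels the middle scan PD, closing the BOR window, or takes the first CR away. A third scan repairs neither.

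The rules can also coexist in two situations. Table 2.3.2-1 scores target CR with non-target lesions not evaluated as PR, so a middle PR can occur with no disease seen. Section 2.3.4 also says that equivocal progression which repeat scans do not confirm is not PD. Both points stand and narrow the problem. Neither is given as the meaning of CR, PR, CR, and neither covers a middle scan on which disease is clearly seen. Section 5.4 adds that progression need not be confirmed.

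A reader might infer that nodes drifting around the 10 mm limit would trigger the conflict routinely. The documents do not support that. Target-lesion PD in Appendix 3, Section 2.1, needs an absolute increase of at least 5 mm, and a node going from 9 to 11 mm rises by 2 mm. Section 2.3.3 also has sub-10 mm nodes recorded so that nodal progression is not overstated. A reader might also infer that CRR, ORR, DOR and PFS all move together, or that DOR would be cut to a single scan interval. The tables above show otherwise.

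Finally, the independent radiology review committee (IRRC) charter was not among the documents supplied and may contain a rule. Disagreement between investigator and IRRC reads is therefore possible but not shown. The inconsistency within Appendix 3, which governs the investigator reads, remains.

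**Conclusion.** The inconsistency is real but narrow. It arises when disease is seen at a scan between two CRs and neither the unevaluated-lesion case nor the unconfirmed equivocal-progression case applies. CRR then depends on an unstated choice of rule, by 2.1, 2.5 or 3.3 points per affected subject. PFS, ORR and DOR are affected only under the conditions listed above.

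The total effect cannot be calculated, because the documents do not say how often such sequences occur. Disease would have to be seen after a CR and be gone again at the next scan, so the number is probably small; that is a judgement, not a figure from the plan. The boundary examples show what any one reclassified subject can do. They are not evidence that a decision in this trial turned on this rule. CRR is an estimate with an interval and carries no test. The point is worth settling because a characterisation of the primary endpoint should not rest on a reader's or programmer's choice.

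**What to change.** In Appendix 3, Section 2.3.4, limit confirmation of CR across an intervening PR to scans where no disease is seen, such as target CR with non-target lesions not evaluated (Table 2.3.2-1). Then add a precedence rule along these lines:

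> When disease is seen at the intervening scan, footnote a to Table 2.3.3-1 governs. If the disease is judged to have been present at the first CR, that CR is re-designated PR, and a later CR needs its own confirmation at least 28 days apart. If disease has truly reappeared, the scan is PD, subject to the existing rule for equivocal progression.

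The separate confirmation adds no new requirement; it follows from the 28-day rule already in Section 2.3.3. Apply the same wording to investigator and IRRC reads, and program BOR accordingly.

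The cost is a few sentences, one derivation rule and a matching line in the IRRC charter. CRR may be slightly lower. Readers must still judge whether disease persisted or reappeared, so PR versus PD can still differ between them, but neither call would produce a confirmed CR from this sequence.
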